Immediately prior to operation, after the induction of anesthesia in the operating room, up to 1cc of 0.5% ICG solution will be injected subdermally or intradermally close to, above the tumor, into the subareolar region or into the periareolar region after disinfection of the breast skin. ICG movement will be facilitated by manual massage and monitored with fluorescence imaging. ICG fluorescence will be elicited and detected by PDE camera (Hamamatsu Photonics, Hamamatsu, Japan) which has FDA 510(k) clearance to visualize ICG fluorescence in the humans for vascular imaging. The lymphatic drainage, made evident by the fluorescent dye, will be monitored in real time on a monitor. The fluorescence will be followed towards the axilla and time for the fluorescence to reach the axilla will be recorded. In accordance with standard practice, an incision will be made in the axilla. Fluorescent lymph nodes (ICG positive) will be localized and removed and sent for pathologic analysis as per standard surgical practice. Node removal will continue until no residual fluorescence is visible in the axilla. Excised nodes will be tested for radioactivity using a standard gamma-detecting probe and the counts per minute will be recorded. Finally, the axillary region will be inspected with the gamma probe to determine if there are any residual radioactive nodes. Residual sentinel nodes will be removed. With regard to radioactivity, sentinel nodes are defined as any node with at least 10% of the hottest nodal counts.

The following information will be collected for each removed node:

1. Fluorescence (yes/no)
2. Counts per minute
3. Pathologic status of node (no metastasis, isolated tumor cells, micrometastasis, macro-metastasis)

Also collected will be procedure related data including transit time to axilla from time of injection, size of tumor, location of tumor, tumor histology, breast size, patient age, BMI.

Consent:

All subjects for this study will be provided a consent form describing this study and providing sufficient information for subjects to make an informed decision about their participation in this study. The formal consent of a subject, using the IRB-approved consent form, will be obtained before that subject is submitted to any study procedure. Consent will be obtained by the study coordinator or investigator of the study in the breast clinic on Main Campus at Cleveland Clinic. Consent will be documented in the medical record.

Finance:

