that the difference between the proportions is greater than the upper equivalence margin: null hypothesis B: $P_{\text{ICG}} - P_{\text{Tc}} \geq +\delta$ which, if rejected, permits the conclusion $P_{\text{ICG}} - P_{\text{Tc}} \leq +\delta$.

Hypotheses A and B will be tested by comparing a two-sided 90% confidence interval (CI) for the difference in the proportions of SNs flagged by the two methods, with the 5% equivalence region ($-\delta$, $+\delta$). Tests for equivalence will be based on the methods for analyzing clustered paired binary data described in Obuchowski(13). To conclude for equivalence the 90% CI needs to be contained entirely within the defined equivalence region, which is equivalent to both null hypotheses (A) and (B) being rejected.

To estimate the number of SNs that will need to be examined, we assumed a detection rate $(A + B)/N$ of 97% for the Tc method, a discordance rate between the two methods $(B + C)/N$ of 6%, and set δ at 5%. We found through simulation that 255 SNs will give adequate power (>80%) to demonstrate equivalence between the two methods, with a type I error (α) rate of 5%. This is estimated to require ~130 patients as the average SN yield is expected to be approximately 2 per patient.

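### Does the unstated within-patient correlation undermine the claim of more than 80% power at 255 sentinel nodes?

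*Combined protocol and SAP*

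**What the plan says.** All of the relevant text is in section 7.0, apart from the node definition in section 3.0.

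- Planning inputs: "we assumed a detection rate $(A + B)/N$ of 97% for the Tc method" and "a discordance rate between the two methods $(B + C)/N$ of 6" per cent, with an equivalence margin of 5 percentage points either way.
- Result of the simulation: "255 SNs will give adequate power (>80%) to demonstrate equivalence between the two methods, with a type I error (α) rate of 5" per cent.
- Conversion to patients: "This is estimated to require ~130 patients as the average SN yield is expected to be approximately 2 per patient".
- Analysis: "Tests for equivalence will be based on the methods for analyzing clustered paired binary data", with a literature reference for the method.
- Decision rule: "Hypotheses A and B will be tested by comparing a two-sided 90% confidence interval (CI) for the difference in the proportions of SNs flagged". The interval must lie wholly inside the margins, which the plan equates with rejecting both one-sided null hypotheses.
- Node definition (section 3.0): "With regard to radioactivity, sentinel nodes are defined as any node with at least 10% of the hottest nodal counts".

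The plan does not give a within-patient correlation, a distribution of nodes per patient or the interval formula in symbols. Nor does it say whether the simulation used clustered data and the cited method.

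**The concern.** The analysis is clustered, but the sample size is described only at node level. Nodes are turned into patients by dividing by about 2 (255/2 = 127.5, hence about 130), and this step does not show whether clustering is already inside the 255. If the simulation took nodes as independent, positive correlation within patients would lower the true power below the simulated value. There is reason to expect some dependence: one ICG injection serves all of a patient's nodes, and Tc status is judged against that patient's hottest node.

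The interval formula matters as well. Once some correlation is present, the choice between a plain normal interval and a more conservative one can move power across 80%. The 5% could also be read either as a nominal level or as an error rate observed in the simulation, and for some formulas the two differ. At stake would be an underpowered equivalence study and, in a borderline result, a conclusion that depends on which interval was used.

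**Working it through.** **Inputs from section 7.0.** Tc detection is 97%, so C/N = 3%. Discordance is 6%, so B/N = 6% − 3% = 3% and the true difference is 0. The margin is 0.05, N = 255, and the interval is a two-sided 90% CI (z = 1.645).

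**Reproducing the plan's figure, independent nodes.** The standard error is √(0.06/255) = 0.01534, and 0.05/0.01534 = 3.260. Power = 2Φ(3.260 − 1.645) − 1 = 89.4%. Exact trinomial enumeration gives:

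| 90% interval | Power at 255 nodes |
|---|---|
| Normal (Wald) | 88.2% |
| Plus-one adjusted Wald | 85.8% |
| Score | 83.2% |
| Wald with 1/N continuity correction | 81.3% |

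Every form exceeds 80%, so the stated claim reproduces.

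**Room for clustering.** By the normal approximation, 80% power needs (1.645 + 1.282)² × 0.06/0.05² ≈ 206 nodes. The 255 therefore carry a design effect of 255/205.5 = 1.24. With two nodes per patient the design effect is 1 + ρ, so this corresponds to ρ of about 0.24. The plan does not say that 255 was built this way, but the room is there.

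**Clustered simulation.** Assumptions, none of them from the plan: 128 patients, 255 nodes, cluster-robust variance, B = C = 3%, and either two nodes each or one plus a random number of extra nodes. Ranges cover both node patterns.

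| Assumed correlation | Normal interval | Continuity-corrected interval |
|---|---|---|
| 0.1 | 82–84% | 75–77% |
| 0.2 | 75–80% | 67–72% |
| 0.3 | 70–76% | 61–68% |

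The normal interval crosses 80% at about 0.13 (varying numbers) to 0.2 (two each). With the planned 130 patients and 260 nodes the range is about 0.15 to 0.24. The continuity-corrected interval crosses at only 0.02 to 0.03, but it starts at 81.3% and the plan mentions no such correction.

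**Effect of the hottest-node rule.** Under section 3.0 the hottest node always meets the 10% threshold. In a patient with any Tc uptake, the nodes therefore cannot all be Tc-negative and ICG-positive. That limits clustering of type C discordance. Suppose there is no complete Tc failure, the hottest node is never type C, and only type B results are shared between two nodes (128 patients). Correlations of 0.1, 0.2 and 0.3 among type B results then amount to about 0.04, 0.09 and 0.14 overall. Normal-interval power is about 86%, 85% and 83%; with the continuity correction it is 81%, 78% and 76%.

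**The 5%.** A 90% CI held inside both margins is two one-sided tests at a nominal 5% each. For the actual error at a 5-point difference with Tc kept at 97%, C = 3%, B = 8% and discordance is 11%. With independent nodes the error is 5.8% (normal), 4.6% (score) or 3.9% (continuity-corrected). For the normal interval at correlations of 0.1 to 0.2 it is 5.8% to 6.1%. Larger values (7.7% independent, 7.8% to 8.7% correlated) arise for the normal interval at B/C = 5.5%/0.5% or the reverse. These imply Tc detection of 99.5% or 94.5%, not the planned 97%.

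**The case for a change.** The strongest case for acting is that the plan itself treats nodes as correlated, so its power statement should show what correlation was assumed. A citation for the test cannot supply that value, and it does not establish that the simulation used the same method. At a correlation of 0.1, the unwritten formula alone decides whether power lies above 80% (82–84%) or below it (75–77%). Fixing the formula before the data are seen would also remove any later choice of interval in a borderline case.

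Part of this stands. The correlation and the node distribution are missing, and the simulation cannot be repeated exactly. Power would also fall below 80% if correlation were well above 0.2.

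The rest is weaker. The interval method is named by citation; whether the source settles the variance and any correction cannot be judged from the documents. The steepest loss of power depends on a continuity correction that the plan never mentions. Finally, correlation that was not foreseen would reduce the chance of showing equivalence, but the planned analysis would still reflect it, because its variance comes from the clustered data and not from the planning assumption.

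**Conclusion.** This is a reporting gap that analysts can fill sensibly, and no change to the plan is needed. The claim of more than 80% power is correct for independent nodes under every interval form tried (81% to 88%). With a cluster-adjusted normal interval it holds up to a correlation of about 0.13 to 0.2. The 5% is read as the nominal level of each one-sided test, as the 90% interval rule implies.

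Supplying the missing settings would document the simulation. It would not alter the margin, the test, the decision rule or the planned number of patients, so the trial's result and conclusion would be the same. The conclusion rests on B = C = 3%, about 2 nodes per patient and a modest within-patient correlation. The correlation range of 0 to 0.3 and the node distributions are assumptions of this check, since the plan gives none.

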7.0 STATISTICAL CONSIDERATIONS

Sample size:

The study will be designed to determine whether ICG based axillary sentinel lymph node biopsy yields a similar number of nodes as ^{99m}Tc sulfur colloid lymph node biopsy. While SLN identification using ^{99m}Tc sulfur colloid is a common technique, neither of the two methods used in this study can be assumed to identify the “correct” set of nodes as sentinel. Therefore, for the purposes of this study, the sentinel status of a node will be defined as being flagged as sentinel by either one or both of the ICG or ^{99m}Tc methods. By this definition, sentinel nodes identified by ^{99m}Tc but not ICG are an error by omission for the ICG method and nodes flagged by ICG but not ^{99m}Tc are an error by the ^{99m}Tc method.

Let A be the number of Tc-positive and ICG-positive SNs detected, B be the number of Tc-positive and ICG-negative SNs detected, and C be the number of Tc-negative and ICG-positive SNs detected. The total number (N) of SNs detected is therefore $N = (A + B + C)$; the proportion of SNs (P_{Tc}) detected by the Tc method is $(A + B)/N$; and the proportion of SNs (P_{ICG}) detected by the ICG method is $(A + C)/N$.

As significant differences in the numbers of nodes identified by each method would have implications regarding the safety of ICG as a radiotracer, the null hypothesis is that the two methods identify an equivalent nodes of nodes as being sentinel nodes. Here equivalence is defined as the difference in the proportions of nodes flagged between the ^{99m}Tc and ICG methods falling within an interval $(-\delta, +\delta)$, where δ is taken to be 5%. Formally the null hypothesis for equivalence is:

$$P_{\text{ICG}} - P_{\text{Tc}} < -\delta \text{ and } P_{\text{ICG}} - P_{\text{Tc}} \geq +\delta$$

If the null hypothesis is rejected we may conclude for the hypothesis of equivalence that:

$$\delta < (P_{\text{ICG}} - P_{\text{Tc}}) < \delta$$

The equivalence hypothesis can be transformed into two one-sided hypotheses:

(A)

that the difference between the proportions is beyond the lower equivalence margin: null hypothesis A: $P_{\text{ICG}} - P_{\text{Tc}} < -\delta$, which, if rejected, permits the conclusion $P_{\text{ICG}} - P_{\text{Tc}} \geq -\delta$

(B)

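### The stated 5% type I error is not shown to be achieved: an ordinary uncorrected 90% interval would give about 6% to 10% at the −5% margin, depending on discordance there

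*Combined protocol and SAP*

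**What the plan says.** All the relevant text is in section 7.0, Statistical Considerations, under Sample size.

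- Margin: equivalence concerns the difference between the ICG and Tc detection proportions, "where δ is taken to be 5" per cent.
- Decision rule: the two one-sided hypotheses "will be tested by comparing a two-sided 90% confidence interval (CI) for the difference in the proportions of SNs flagged by the two methods" against that region. "To conclude for equivalence the 90% CI needs to be contained entirely within the defined equivalence region".
- Method: "Tests for equivalence will be based on the methods for analyzing clustered paired binary data", with a literature reference. The plan does not say whether the interval is Wald, score or continuity-corrected.
- Planning values: a Tc detection rate "of 97% for the Tc method, a discordance rate between the two methods" "of 6%, and set δ at 5" per cent.
- Claim: simulation showed that 255 nodes (about 130 patients with about 2 nodes each) give power above 80% "to demonstrate equivalence between the two methods, with a type I error (α) rate of 5" per cent.

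No simulated rejection rate at a true difference of ±5% is reported. No within-patient correlation is given, and nothing is said about what discordance or Tc rate would apply at the margin.

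**The concern.** A 90% interval inside ±5% is the standard form of two one-sided 5% tests, so 5% is the nominal level. Whether it is the actual level depends on how good the interval is with few informative observations. Only discordant nodes carry information on the difference, and the plan expects about 0.06 × 255 = 15.3 of them.

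An uncorrected interval takes its standard error from those same nodes. When ICG is truly 5 points worse but looks better by chance, few discordant nodes are seen. The estimated standard error then shrinks with the estimate, so the interval is too short just when a false claim is possible.

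Section 7.0 links differences between the methods to safety, and this is the only test in the plan. A false equivalence claim is therefore the error that matters most.

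**Working it through.** **Inputs.** From section 7.0: N = 255, δ = 5%, 90% interval, Tc rate 97%, discordance 6%, about 130 patients with about 2 nodes each. Assumed: interval = estimate ± 1.645 SE; within-patient correlation 0 to 0.3.

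**Formulae.** B counts Tc-only nodes and C counts ICG-only nodes. D = (C − B)/N and SE² = [(B + C)/N − D²]/N. Every counted node is flagged by at least one method, so the Tc rate is 1 − C/N.

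**Reproducing the plan's power.** A Tc rate of 97% gives C/N = 3%. Discordance of 6% then gives B/N = 3% and a true difference of 0.
- Normal approximation: SE = √(0.06/255) = 0.01534, and power = 2Φ(0.05/0.01534 − 1.645) − 1 = 2Φ(1.615) − 1 = 89.4%.
- Exact trinomial enumeration: 88.2% (uncorrected), 83.3% (Tango score), 81.3% (1/N continuity correction).

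All three exact figures fit the claim of more than 80%, so the power figure does not reveal which interval was used.

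**What can hold at the margin.** The two planning values imply a zero difference, so both cannot hold at −5%. Holding discordance at 6% forces B = 5.5%, C = 0.5% and a Tc rate of 99.5%. Holding Tc at 97% forces C = 3%, B = 8% and discordance of 11%. With Tc at 97% the difference cannot exceed +3%, so only the lower margin is reachable.

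**Type I error at −5%, exact enumeration, 255 independent nodes.**

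| B/N, C/N | Tc rate | Discordance (expected nodes) | Uncorrected | Tango score |
|---|---|---|---|---|
| 5%, 0% | 100% | 5% (12.8) | 10.6% | 5.7% |
| 5.5%, 0.5% | 99.5% | 6% (15.3) | 7.7% | 4.6% |
| 6%, 1% | 99% | 7% (17.9) | 6.8% | 4.6% |
| 8%, 3% | 97% | 11% (28.1) | 5.8% | 4.6% |
| 10%, 5% | 95% | 15% (38.3) | 5.1% | 4.2% |

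A variance computed under equality gives the same uncorrected figures at 255 nodes. At 260 nodes the 5%, 6% and 11% discordance rows become 9.4%, 7.4% and 6.0%.

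**Hand check of the first row.**
- With C = 0 and B = 8, D = −8/255 = −3.14%, SE = 1.09% and the lower limit is −3.14% − 1.645 × 1.09% = −4.93%. Equivalence is declared.
- With B = 9 the limit is −5.43%, so it is not. The error is therefore P(Bin(255, 0.05) ≤ 8) = 10.6%.
- The score test uses the SE under the margin, √(0.05 × 0.95/255) = 1.365%. B = 8 gives (5 − 3.14)/1.365 = 1.36, below 1.645. B = 7 gives (5 − 2.745)/1.365 = 1.652, just above it. The error is P(Bin(255, 0.05) ≤ 7) = 5.7%.
- The uncorrected SE at B = 8 is 1.09/1.365 = 80% of the SE under the margin.

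**Clustering.** Simulations used 130 patients averaging 2 nodes, a cluster-robust variance and correlation 0 to 0.3. The uncorrected interval gave 7.8% to 9.3% at 6% discordance with varying node numbers, 7.4% to 8.6% with exactly two nodes per patient, and about 6% with Tc at 97%. A score interval inflated by the ratio of clustered to unclustered variance gave 4.3% to 5.7% for correlation 0 to 0.2, and up to 6.6% at 0.3.

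**The case against.** The strongest objection is that the interval tested here is assumed. The plan cites a method whose source is not available for this review and never says that the interval is uncorrected. A continuity-corrected interval would give 4.6% at 6% discordance with 81.3% power, which agrees with both stated figures. This stands: the documents do not establish that the 5% is missed. It does not close the point, because no correction is stated and the ordinary reading of the rule exceeds 5% at every discordance from 5% to 11%.

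Second, a reader might infer from the 6% discordance row that false equivalence occurs 1.5 to 2 times as often as stated under the plan's own inputs. The documents do not support that. Keeping 6% at the margin drops the planned 97%; keeping 97% leaves an excess of about one point or less. The 10.6% case needs Tc to miss nothing and is sensitive to discreteness (9.4% at 260 nodes).

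Third, the quoted 5% can be read as the nominal level of a correctly formed 90% interval rule. That is a fair reading, but the plan does not call it nominal and reports no achieved rate beside its simulated power.

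Fourth, a better interval might be presented as costless. It is not: 83% power holds for independent nodes only, and the score interval falls below 80% at a correlation of 0.1, where the uncorrected interval still meets the target.

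**Conclusion.** The concern holds in a limited form, as something that should be fixed. The plan states a 5% type I error without showing that its rule achieves it. If the interval is estimate ± 1.645 SE, the rate at the −5% margin with 255 independent nodes is about 6% with Tc at 97%, 7.7% with discordance at 6%, and at most 10.6% in the extreme case examined. Under assumed correlations of 0 to 0.3 it is roughly 7.5% to 9.5% at 6% discordance and about 6% with Tc at 97%. The direction is consistent across 5% to 11% discordance; the size depends on which planning value is kept at the margin, and the plan does not say. The conclusion rests on the assumed interval form and, for the clustered figures, on correlations that the documents do not give.

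**What to change.** In section 7.0:

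1. Name the interval: a score-type (Tango) 90% interval, with the variance restricted to a difference of ±δ and inflated by the ratio of clustered to unclustered variance. Keep the ±5% rule.
2. Beside the power, report the simulated type I error at ±5%, with the discordance, Tc rate and within-patient correlation assumed there.
3. Restate the >80% power with its correlation assumption.
4. If an uncorrected interval is kept, give its type I error as about 6% to 10%, depending on discordance at the margin, in place of 5%. If a correction is already intended, say which one and give its achieved rate.

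The cost is wording, a short simulation and some power. At the planned size, power falls from about 88% to 83% with independent nodes, from about 83% to 77% at correlation 0.1, and from about 77% to 69% at 0.2. No patients need be added to make the change, but keeping power above 80% under even modest correlation may require more nodes. The sponsor should make that choice openly.
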